6.1.2 Health, hospitalisation and referral outcomes

6.1.2.1 Proportion of children with a severe complication by Day 7

Severe complication is defined as death or secondary hospitalisation. Secondary hospitalisation refers to any delayed hospitalisation (occurring at any point greater than 24hrs after the Day 0 consultation) and any hospitalisation occurring without a referral.

Information on death and hospitalisation will be taken, in order, from:

- ξ Day7 follow-up assessment
- ξ If Day7 follow-up assessment is missing, Day28 follow-up assessment

Death will be counted in the numerator if death date is within 7 days of Day0 (7th day included). Hospitalisation will be counted in the numerator if the child was not referred at Day0 or hospital admission date is within 7 days of Day0 (7th day included) but after 24hrs of Day0.

The denominator will be all children recruited. Children for whom no death and hospitalisation data are available or withdrew prematurely from the study will be assumed to be alive and not hospitalised by Day7.

6.1.2.2 Proportion of children with a severe complication by Day 28

Severe complication is defined as per the outcome above.

Information on death and hospitalisation will be taken, in order, from:

- ξ Day7 follow-up assessment
- ξ If Day7 follow-up assessment is missing or no outcomes were reported, Day28 follow-up assessment
- ξ If both Day7 and Day28 assessments are missing or no outcomes were reported, unscheduled visits (deaths only)

Death will be counted in the numerator if death date is within 28 days of Day0 (28th day included). Hospitalisation will be counted in the numerator if the child was not referred at Day0 or hospital admission date is within 28 days of Day0 (28th day included) but after 24hrs of Day0.

The denominator will be all children recruited. Children for whom no death and hospitalisation data are available or withdrew prematurely from the study will be assumed to be alive and not hospitalised by Day28.

6.1.2.3 Proportion of children admitted to hospital within 24 hours of Day 0 consultation and as a result of a referral

Information on hospitalisation will be taken, in order, from:

- ξ Day7 follow-up assessment
- ξ If Day7 follow-up assessment is missing, Day28 follow-up assessment

Hospitalisation will be counted in the numerator only if the child received a referral advice (as per definition above) at Day0 and hospital admission date is within the end of the following day. The denominator will be all children recruited.

Additionally, the proportion will be calculated and reported using only children who were referred as denominator.

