3.8 Timing for Baseline and Outcome Assessments

Baseline is defined as the date of enrolment (Day 0) and time will be measured from this point.

Follow-up will occur 7 days and 28 days after Day 0. As defined in the protocol, no time window applies to Day 7 follow-up and a window of + 7 days applies to Day 28 follow-up. Refer to “Participants timeline” section of the protocol for more details.

The components (i.e. death and hospitalisation) required for the analysis of the primary outcomes will be assessed at both Day 7 and Day 28 follow-ups. For the main analysis, date of death and date of hospitalisation will be used irrespective of when these information are collected.

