6.1.1 General definitions

Day 7 / Day 28 assessment

Day 7 / Day 28 assessment refers to information reported by the caregiver after Day 0 and recorded in Day 7 / Day 28 forms. Data collected as part of unscheduled visits are also integrated in these forms.

If multiple successful follow-up assessments for the same child are recorded within Day7 or Day28 databases, the most recent follow-up assessment within each database will be used. To limit potential recall bias, assessments conducted far beyond the expected follow-up time will be dropped. This will be 30 and 60 days from Day 0 for Day 7 and Day 28 respectively.

Death

A child will be considered deceased if, from Day 7 / Day 28 assessment, his/her status at the time of follow-up is “deceased”. In case of implausible death date (i.e. prior to enrolment date), death will be handled as follow:

- ξ if death date is recorded at Day7 follow-up, death will be assumed to be within 7 days of Day0
- ξ if death date is not recorded at Day7 follow-up but only at Day28 follow-up, death will be assumed to be after 7 days of Day0 but within 28 days.

Hospitalisation

A child will be considered hospitalised if, from Day 7 / Day 28 assessment, he/she went to a hospital, was admitted overnight or if his/her status at the time of follow-up is “hospitalised”. In case of implausible hospitalisation date (i.e. prior to enrolment date), hospitalisation will be handled as follow:

- ξ if hospitalisation date is recorded at Day7 follow-up, hospitalisation will be assumed to be within 7 days but after 24hrs of Day0
- ξ if hospitalisation date is not recorded at Day7 follow-up but only at Day28 follow-up, hospitalisation will be assumed to be after 7 days of Day0 but within 28 days.

Hospitalisation within 24hrs of Day0

For the purpose of primary analysis, a child will be considered admitted to hospital 24hrs of Day0 consultation if the date of hospitalisation is the same as Day0 date or is one day after Day0 date.

Referral

A child will be considered to be referred (either to a hospital or to an inpatient part of a larger primary healthcare facility) if, at Day0, the caregiver confirms that the child was urgently referred or the research assistant confirms that an urgent referral advice was recorded for the child. If urgency is unknown from both sources, referral will be assumed to be urgent.¹

Antibiotics

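### SAP 3.8 and SAP 6.1.2.1/6.1.2.3 treat an in-window event first reported at Day 28 differently, and protocol 8.1.1 gives a third source rule for the primary outcomes

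*SAP*

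**What the plan says.** Three places set the source of the primary outcomes.

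- **SAP 3.8.** Death and hospitalisation for the primary outcomes "will be assessed at both Day 7 and Day 28 follow-ups". The section continues: "For the main analysis, date of death and date of hospitalisation will be used irrespective of when these information are collected".
- **SAP 6.1.2.1 (severe complication by Day 7) and 6.1.2.3 (admission within 24 hours after referral).** Information is taken in order: the Day 7 form first, then "If Day7 follow-up assessment is missing, Day28 follow-up assessment". The numerators themselves work by event date. For death in 6.1.2.1: "Death will be counted in the numerator if death date is within 7 days of Day0 (7th day included"). For 6.1.2.3 the child must have been referred and "hospital admission date is within the end of the following day".
- **Protocol 8.1.1 (Follow-up).** Both primary outcomes rest on the Day 7 contact; the Day 28 interview serves the Day 28 secondary outcome.

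For the Day 28 secondary outcome, SAP 6.1.2.2 uses a wider trigger: "If Day7 follow-up assessment is missing or no outcomes were reported, Day28 follow-up assessment".

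**The concern.** Two programmers working from the same SAP could build different primary datasets. Under 3.8 a dated event counts whichever form carries it. Under 6.1.2.1 and 6.1.2.3 a completed Day 7 form closes the question, even if the Day 28 form dates an event inside the window. The wider trigger in 6.1.2.2 shows that the SAP distinguishes the two rules and gives the narrower one to the primary outcomes.

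At stake are an unambiguous derivation of both primary outcomes and some undercounting of a rare event. The planned sensitivity analyses would not show it. They vary encounters, hospitalisation cut-offs, referral definitions and the handling of children lost to follow-up or withdrawn. A child with a Day 7 form is not missing, and no planned analysis pools the two forms.

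**Working it through.** **1. The same child under each rule.** Take a child with a completed, event-free Day 7 form and a Day 28 form giving a death dated Day 7.

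| Rule | Result |
|---|---|
| SAP 3.8 | event by Day 7 |
| SAP 6.1.2.1 | non-event (Day 7 form is not missing) |
| SAP 6.1.2.2 | event by Day 28 (Day 7 form reported no outcome) |
| Protocol 8.1.1 | non-event (Day 7 contact only) |

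**2. Does another rule recover the event?** SAP 6.1.1 settles duplicates separately for each follow-up: "the most recent follow-up assessment within each database will be used". It does not merge Day 7 with Day 28. Its rule for events recorded only at Day 28 covers implausible dates, not valid ones. So nothing recovers it.

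**3. How such cases arise.**
- *6.1.2.1:* the window includes the whole of Day 7, but a call on Day 7 ends observation at that hour. The Day 7 respondent may also not report an event; protocol 6.5.1 allows another caregiver to answer after the initial call.
- *6.1.2.3:* the window closes at the end of the day after Day 0, so a call on Day 7 cannot precede a qualifying admission. Only discordant reporting remains.

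**4. Share of Day 2–7 events after a midday Day 7 call (hypothetical).** The window is 6 days and the call comes at 5.5 days.
- Constant rate: 0.5/6 = 8.3%.
- Rate halving every h days: (2^(−5.5/h) − 2^(−6/h)) / (1 − 2^(−6/h)).
  - h = 3: (0.2806 − 0.2500)/0.7500 = 4.1%
  - h = 2: (0.1487 − 0.1250)/0.8750 = 2.7%
  - h = 1.5: (0.0787 − 0.0625)/0.9375 = 1.7%

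The half-lives are assumptions; the documents give none.

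**5. Reproducing the plan's power (SAP 3.4, Tanzania).** Inputs: 22 clusters × 1,680 = 36,960 per arm; ICC 0.001; 1.1% against 0.77%; alpha 0.05, taken as two-sided.
- Design effect = 1 + 1,679 × 0.001 = 2.679; effective n = 36,960/2.679 = 13,796 per arm.
- Power = Φ[(|p1 − p2|√n − 1.96√(2p̄q̄)) / √(p1q1 + p2q2)] = Φ[(0.3876 − 0.2668)/0.1361] = Φ(0.888) = 81.3%.

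This agrees with the stated 80%.

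**6. Effect of losing a share f of all severe complications, equal in both arms.** Both proportions are multiplied by (1 − f). Expected events are 36,960 × 0.011 = 407 (control) and 36,960 × 0.0077 = 285 (intervention).

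| Assumed f | Uncounted, control / intervention | Power, Tanzania |
|---|---|---|
| 0 | 0 / 0 | 81.3% |
| 2% | 8 / 6 | 80.5% |
| 5% | 20 / 14 | 79.3% |
| 10% | 41 / 28 | 77.1% |

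At f = 2% the loss is 81.3 − 80.5 = 0.8 points. In India, with 60 clusters of 510 per arm, the same 2% moves power from 93.2% to 92.8%.

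**The case against.** **Protocol 8.1.1 supports the narrower rule.** It ties both primary outcomes to the Day 7 contact, and SAP 1.1 says the SAP follows the protocol unless it says otherwise. This stands in part: 6.1.2.1 is closer to the protocol than 3.8 is. But 6.1.2.1 already departs from the protocol by using Day 28 when Day 7 is missing, so it does not settle the matter.

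**SAP 3.8 may mean only that the event date, not the call date, decides within whichever form is selected.** That would dissolve most of the conflict, but it sits badly with the statement that components are assessed at both contacts and that the time of collection is irrelevant.

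**Day 7 precedence may be deliberate.** SAP 6.1.1 limits recall bias by dropping late assessments, yet keeps Day 28 forms up to 60 days after Day 0. Pooling could bring in later events misdated into Days 0–7. This stands as a real cost of the fix.

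**Stronger readings that the documents do not support:**
- *Both primary outcomes are equally affected.* The time-of-call route cannot reach 6.1.2.3.
- *Some 34 Tanzanian control events would be lost (8.3% of 407).* That needs every completed call at midday on Day 7, a constant rate and all 407 events on Days 2–7. Protocol 6.5.1 allows repeat calls on later days and then in-person follow-up, and any contact after Day 7 closes the gap.
- *These events are lost to the trial.* Where Day 7 reported no outcome, 6.1.2.2 captures severe complications in the Day 28 outcome. The forms themselves are not in the documents, so how fully the Day 28 form asks again about Days 0–7 cannot be seen.
- *The treatment effect is biased.* Unequal losses of 5% and 10% would show a true risk ratio of 0.70 as 0.70 × 0.90/0.95 = 0.66 or 0.70 × 0.95/0.90 = 0.74. But nothing in the documents points to unequal loss, and protocol 7.2 has telephone assessors blinded to arm.

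**Conclusion.** The inconsistency holds on the text: SAP 3.8, SAP 6.1.2.1/6.1.2.3 and protocol 8.1.1 give three source rules for the primary outcomes, and the first two classify the same child differently. It should be settled before analysis, because it concerns the derivation of both primary outcomes.

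The numerical effect is probably small, and its true size is unknown. The 2–8% range is conditional on midday Day 7 calls and covers only Day 2–7 events; calls completed later lower it, and unreported events at Day 7 would add an amount the documents do not give. The 0.8-point power loss rests on an assumed 2% share, equal across arms, applied to all severe complications. No count can be offered for 6.1.2.3. The planned sample-size figures are not in question on this point.

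**What to change.** In SAP 6.1.2.1 and 6.1.2.3, replace the source order with one rule that agrees with 3.8:

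> A death or admission counts if its date falls in the outcome window and it is reported on either the Day 7 or the Day 28 form. If the two forms date the same event differently, the Day 7 date is used.

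Three additions are needed.

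- State that this departs from protocol 8.1.1, and why.
- Because Day 28 dates carry more recall error, report the Day-7-form-first derivation as a sensitivity analysis for both primary outcomes.
- Keep the date condition explicit for every admission. The numerator sentence in 6.1.2.1 can be read as setting no date limit for unreferred admissions, which would matter more once the Day 28 form is read for all children.

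Copying only the wider trigger from 6.1.2.2 would be incomplete. A child whose Day 7 form reports a referred admission within 24 hours, and who dies later on Day 7, would still be missed.

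The cost is SAP wording and a small change to derivation code, with no new data collection. The price is a small risk of counting later events misdated into the window, which the sensitivity analysis would help to show.

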Quantitative research assistants will conduct the phone follow-up interviews using an EDC mobile application. Personally identifiable information (PII) will be used for contacting caregivers. No time window applies to Day 7 follow-up. A window of +7 days applies to Day 28 phone call attempts (Day 28 to Day 35).

Data that will be collected at Day 7 follow-up will include cure status (recovery from illness as reported by the caregiver), death and hospitalization information between Day 0 and Day 7 as

reported by caregivers. The primary outcomes on the proportion of children with severe complications by Day 7 and on the proportion of children admitted to hospital within 24 hours of the Day 0 primary care consultation as a result of a referral will be assessed based on Day 7 follow-up. Hospital name, duration of hospitalization and reason for admission will be collected for children reported to have been hospitalized to facilitate the retrospective data collection at referral hospital level.

Data collected at Day 28 follow-up will include death and hospitalization information as reported by the caregiver. The secondary outcome on the proportion of children with severe complications at Day 28 will be assessed on the basis of this interview.

Higher level of care visit

Data collection will be conducted retrospectively at all government-designated and private referral facilities within the study area, including hospitals or emergency / inpatient area of larger primary or secondary care facilities (e.g., study facilities that can admit paediatric patients). A quantitative research assistant using the EDC mobile application will collect data from referral facility records, registries and discharge summaries to document hospitalization for all children reported to have been hospitalized between Day 0 and Day 7. Personally identifiable information will be collected to cross-check the identity of the patients. Arrival date and time, basic clinical information on arrival and, if admitted, admission and discharge diagnosis, and admission duration and outcome will be collected. If available, data on oxygen saturation at admission, oxygen administration and intensive care unit (ICU) admission and duration will also be recorded.

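### SAP 6.1.2.1 sets no 7-day limit on admissions of children not referred at Day 0, so later admissions can enter the Day 7 primary outcome: a small drafting error to correct before analysis

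*SAP*

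**What the plan says.** Protocol 6.4.2 defines the first primary outcome as death or secondary hospitalisation by Day 7. Secondary hospitalisation means an admission more than 24 hours after the consultation, or any admission without referral.

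SAP 6.1.2.1 turns this into a counting rule. For deaths: "Death will be counted in the numerator if death date is within 7 days of Day0 (7th day included"). For hospitalisations, the event is "counted in the numerator if the child was not referred at Day0 or hospital admission date is within 7 days of Day0", the second condition being further limited to admissions after 24 hours. Children without data are "assumed to be alive and not hospitalised by Day7".

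The source is the Day 7 form, then: "If Day7 follow-up assessment is missing, Day28 follow-up assessment". SAP 6.1.1 drops very late forms: "This will be 30 and 60 days from Day 0 for Day 7 and Day 28 respectively". Protocol 8.1.1 says of the first call: "No time window applies to Day 7 follow-up". It gives Day 28 calls a window of Day 28 to Day 35, and SAP 3.8 repeats both statements.

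**The concern.** The rule has two conditions joined by an or, and only the second carries a date. A child not referred at Day 0 who was admitted on, say, Day 15 meets the first condition and is scored as having a severe complication by Day 7. Coded literally, the outcome's time horizon depends on which form was obtained and on whether the child was referred. Coded by its evident intent, it is seven days for everyone. An SAP should not leave that choice to the programmer for a primary endpoint, and a correction made after results are seen would be harder to defend.

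**Working it through.** **Step 1: the logic.** Let R = referred at Day 0, S = admitted within 7 days, and L = admitted later than the 24-hour definition (SAP 6.1.1: later than the day after Day 0).

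- As written: not R, or (S and L).
- Other possible grouping: (not R or S), and L.
- Evident intent: S, and (not R or L).

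| Referred | Admission day | As written | Other grouping | Intent |
|---|---|---|---|---|
| No | 0 or 1 | counts | no | counts |
| No | 3 or 7 | counts | counts | counts |
| No | 8, 15, 28 or 45 | **counts** | **counts** | no |
| Yes | 0 or 1 | no | no | no |
| Yes | 3 or 7 | counts | counts | counts |
| Yes | 8 or later | no | no | no |

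Neither grouping supplies the limit. The other one also loses unreferred admissions within 24 hours.

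**Step 2: can late admissions reach the rule?** There are two routes.

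- The main route is the Day 28 form replacing a missing Day 7 form.
- The weaker route is a Day 7 form completed between Day 8 and Day 30. Protocol 8.1.1 describes Day 7 data as "death and hospitalization information between Day 0 and Day 7", which narrows this route. It does not close it, because SAP 6.1.1 also treats a child as hospitalised from the state found at contact (the child "was admitted overnight or if his/her status at the time of follow-up is" hospitalised).

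The complete-case set does not remove these children, since SAP 4.3 requires only one completed follow-up.

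**Step 3: is the limit supplied elsewhere?** The title, the death cap and the default for missing children all point to Day 7. SAP 6.1.1 places an implausibly dated admission known only from Day 28 after Day 7, yet 6.1.2.1 would still count it if the child was unreferred. SAP 3.8 says event dates are used whenever they were collected, but states no cut-off. None of these puts a date on the unreferred branch.

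**Step 4: reproduce the planned power.** Inputs from Protocol 6.6.1 and the Summary: 1.1% against 0.77%, alpha 0.05 (taken as two-sided), ICC 0.001; Tanzania 22 clusters of 1,680 per arm; India 40 clusters of 510 initially, later up to 60.

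- Design effect = 1 + (m − 1) × 0.001: Tanzania 2.679, India 1.509.
- Effective n per arm: Tanzania 36,960 / 2.679 = 13,796; India (60) 30,600 / 1.509 = 20,278.
- Power = Φ{[|p1 − p2|√n − 1.96√(2p̄(1 − p̄))] / √(p1(1 − p1) + p2(1 − p2))}.
- Tanzania: (0.3876 − 0.2668) / 0.1361 = 0.888, so power is 81.3%. India: 80.5% with 40 clusters, 93.2% with 60.

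The stated 80% reproduces.

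**Step 5: size of the error.** The documents give no rates, so both are assumed: f = share of children classified from a Day 28 form, and r = risk among them of an unreferred admission after Day 7. The pilot target of 90% reachable by phone on Day 7 (Protocol 6.4.1) suggests 10% as the top of the range for f if that target is met. Added rate = f × r, the same in both arms.

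| f × r | Added (points) | Risk ratio | Extra events per arm, Tanzania | Power, Tanzania | Power, India (60) |
|---|---|---|---|---|---|
| none | 0 | 0.700 | 0 | 81.3% | 93.2% |
| 2% × 0.1% | 0.002 | 0.772/1.102 = 0.701 | 0.7 | 81.2% | 93.2% |
| 5% × 0.2% | 0.010 | 0.780/1.110 = 0.703 | 3.7 | 80.9% | 93.0% |
| 5% × 0.5% | 0.025 | 0.795/1.125 = 0.707 | 9.2 | 80.3% | 92.6% |
| 10% × 0.5% | 0.050 | 0.820/1.150 = 0.713 | 18.5 | 79.3% | 92.0% |

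Planned control events in Tanzania are 36,960 × 1.1% = 407 per arm. At alpha 0.025, the share SAP 4.1 first gives each endpoint, the last row takes Tanzania from 72.8% to 70.3%, a loss of similar size.

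**The case against.** The best defence is that nobody would code it this way. SAP 1.1 says the analysis complies with the protocol unless otherwise detailed, the protocol says Day 7, and every neighbouring rule agrees. That stands as evidence of intent, and it makes this a misplaced clause rather than a changed endpoint. It does not make the counting rule right. Section 6.1.2.1 is the detailed definition, and SAP 1.1 also says the document should let others run the analysis.

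The defence is also right on reach. The Day 28 route opens only after repeat calls, community contacts and, with consent, an in-person visit have failed (Protocol 6.5.1). Planned Day 28 contact ends at Day 35, and Day 60 is only the outer limit for accepting a form. The 10% used as the top of the range includes children never reached, who add no events, and children reached a few days late, who add little time at risk.

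A reader might infer bias between arms, because referral decides whether the limit applies and the intervention is meant to change referral. The documents do not support that. They give no referral rates by arm. If most children in both arms are unreferred (an assumption), the additions are similar in both. Protocol 7.2 also has outcomes collected by callers blinded to arm and facility, which makes a difference in contact timing less likely. A reader might also infer a serious loss of power; that would need rates beyond the range that the 90% target suggests.

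**Conclusion.** The rule is wrong as written on either grouping of the sentence, and it contradicts the outcome's title and its companion rules. SAP 6.1.2.2 has the same error in a secondary outcome: an unreferred admission after Day 28 can count, mainly on Days 29-35 if the call window is kept and up to Day 60 at most. There the Day 28 form is also consulted when the Day 7 form reports no outcome, so the route does not depend on a missed first call.

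The likely effect on the primary result is small: under the assumptions of Step 5, about 1 to 18 extra events per arm in Tanzania and at most 2 points of power at alpha 0.05, with a slight pull of the risk ratio towards 1. The true size is unknown. This is a minor correction, worth making because it concerns a primary endpoint and costs almost nothing.

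**What to change.** - **SAP 6.1.2.1:** count a hospitalisation if admission falls within 7 days of Day 0, counting the seventh day, AND (the child was not referred at Day 0 OR admission was later than the 24-hour definition).
- **SAP 6.1.2.2:** use the same form with 28 days.
- **Only if admission dates can be missing:** the placement rule in SAP 6.1.1 covers only dates before enrolment. Extend it to undated admissions of unreferred children: recorded at Day 7, within 7 days; recorded only at Day 28, after 7 but within 28 days. Do not extend it to referred children, because it would turn their undated admissions into severe complications.

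The cost is one line in each of the two definitions, one conditional line in 6.1.1, and matching code. No new data are needed, since the rules already use admission dates. Make the change before the final analysis.

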6.1.2.4 Average length of stay (in days) of children admitted to hospital

Length of stay is defined as hospitalisation duration in days as reported by the caregiver at Day 7 and Day 28. If a child is hospitalised twice, the first hospitalisation will be used and second hospitalisations will be reported separately. The denominator will be all hospitalised children.

6.1.2.5 Proportion of children referred by a primary healthcare provider to a higher level of care at Day 0 consultation

All children who received a referral advice (as per definition above) at Day0 will be counted in the numerator. The denominator will be all children recruited.

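### Read literally, the SAP's source order for severe complication by Day 28 closes the Day 28 form once Day 7 reports an appropriate admission, so a later death or readmission is not counted

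*SAP*

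**What the plan says.** SAP 6.1.2.2 defines severe complication by Day 28 as death or secondary hospitalisation. It sets an order of sources: "Information on death and hospitalisation will be taken, in order, from" the Day 7 form; then "If Day7 follow-up assessment is missing or no outcomes were reported, Day28 follow-up assessment"; then "If both Day7 and Day28 assessments are missing or no outcomes were reported, unscheduled visits (deaths only"). The SAP does not say what counts as an outcome in these conditions.

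SAP 6.1.1 counts a child as hospitalised if "he/she went to a hospital, was admitted overnight or if his/her status at the time of follow-up is" hospitalised. That covers any admission, whether or not it followed a referral.

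The endpoint is narrower: "Secondary hospitalisation refers to any delayed hospitalisation (occurring at any point greater than 24hrs after the Day 0 consultation"), together with any admission without a referral. A referred admission on Day 0 or the next day is the other primary outcome (appropriate hospitalisation) and is not a severe complication.

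Protocol 8.1.1, on the Day 28 call: "The secondary outcome on the proportion of children with severe complications at Day 28 will be assessed on the basis of this interview". It sets no condition on what Day 7 showed.

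**The concern.** The source list is a stopping rule, not a pooling of forms. If an appropriate admission reported at Day 7 counts as a reported outcome, the Day 28 form is not opened for that child. The child has no severe complication on the Day 7 form. A death on Day 15, for example, would appear only on the Day 28 form, and the child would be counted as event-free. The unscheduled-visit source carries the same condition, so it does not rescue the event.

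Children admitted on referral within a day are among those the trial expects to be most severely ill, so their later deaths and readmissions are events this outcome is meant to capture. The intervention also aims to enlarge this group. If it does, the loss need not be equal between arms.

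**Working it through.** **Which children are exposed.** Consider what the Day 7 form can show under the literal rule.

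| Day 7 form shows | Day 28 form read? | Later event lost? |
|---|---|---|
| No form | Yes | No |
| No death, no admission | Yes | No |
| Death, or secondary hospitalisation | No | No, child already counts |
| Only a referred admission within 24 h | No | Yes |

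Only the last row loses events. The window runs from the actual Day 7 call to Day 28. SAP 3.8 sets no time window for the Day 7 call, and SAP 6.1.1 accepts it up to 30 days after Day 0.

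**Inputs** (SAP 3.4, protocol 6.6.1): appropriate hospitalisation 1.5% in control with a 30% relative increase, so 1.5% × 1.30 = 1.95%; severe complication by Day 7 1.1% v 0.77%; ICC 0.001; Tanzania 22 clusters of 1,680 per arm; India 40 clusters of 510 per arm initially, then up to 60. Two-sided alpha 0.05 is used, as the documents do not state sidedness for the sample size.

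**The plan's own sizes reproduce.** Per arm before clustering: (1.960 + 0.842)² × (0.011 × 0.989 + 0.0077 × 0.9923) / 0.0033² ≈ 13,348.

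- Tanzania: design effect 1 + 1,679 × 0.001 = 2.679; 13,348 × 2.679 / 1,680 = 21.3, rounded up to 22 clusters, and 22 × 1,680 = 36,960.
- India, initial: design effect 1.509; 13,348 × 1.509 / 510 = 39.5, rounded up to 40 clusters, and 40 × 510 = 20,400.

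**Exposed children per arm** = N × appropriate-admission rate:

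- Tanzania: 36,960 × 1.5% = 554 control; 36,960 × 1.95% = 721 intervention.
- India, 40 clusters (20,400): 306 v 398.
- India, 60 clusters (30,600): 459 v 597.

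**Missed events** = exposed children × q, where q is the risk of death or readmission after the Day 7 call and by Day 28. The documents give no q, so it is assumed, equal in both arms. Bias in the risk difference = (1.95 − 1.50) × q percentage points.

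| q (assumed) | Tanzania missed, control v intervention | Bias, percentage points |
|---|---|---|
| 1% | 5.5 v 7.2 | 0.0045 |
| 5% | 27.7 v 36.0 | 0.0225 |
| 10% | 55.4 v 72.1 | 0.045 |

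These counts take both calls as completed for every exposed child. A child missed at Day 7 is not exposed, because the Day 28 form is then read. A child missed at Day 28 has no form to recover the event from.

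**Scale.** The documents give no Day 28 event rates. If the rule produced 1.1% v 0.77% (risk ratio 0.70), adding back the missed events gives (0.77 + 1.95q) / (1.1 + 1.5q), with rates in percent and q as a proportion: 0.708, 0.738 and 0.772 for q = 1%, 5% and 10%.

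**When the loss favours the intervention.** This requires 1.95 × q(intervention) > 1.5 × q(control), that is, a ratio of later risks above 1.5 / 1.95 = 0.77. If admissions do not rise and later risks are equal, the loss is the same in both arms.

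**The case against.** The strongest reply is that an outcome in this condition means a severe complication. SAP 6.1.2.2 opens by defining severe complication with reference to the preceding outcome, and the extra condition is absent from 6.1.2.1, so it may have been added simply to follow event-free children to Day 28. On that reading the Day 28 form is read for an appropriately admitted child and nothing is lost. SAP 6.1.1 also provides for deaths recorded only at Day 28, and SAP 1.1 claims compliance with the protocol unless stated otherwise. This stands as a possible intention. But the lead-in to the list names death and hospitalisation, 6.1.1 defines hospitalisation as any admission, and SAP 1.1 wants others to be able to run the analysis. Two programmers could reach different counts.

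A reader might also infer more than the documents support:

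- *That the comparison is biased towards the intervention by design.* A 30% rise in appropriate admissions is the trial's hypothesis, not a design feature, and the direction also depends on later risks.
- *That SAP 3.8 contradicts the Day 28 rule directly.* It says that "date of death and date of hospitalisation will be used irrespective of when these information are collected", but that paragraph concerns the components of the primary outcomes. It supports the point by analogy only; the direct conflict is with protocol 8.1.1.
- *That the Day 7 primary outcome loses events in the same way.* No loss is shown there, since a Day 7 call made on or after Day 7 already covers that window.
- *That every event on Days 8 to 28 is at risk.* Only those after the actual Day 7 call are.
- *That second admissions are set aside throughout.* The statement that "second hospitalisations will be reported separately" belongs to the length-of-stay outcome.

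It is also fair to say that this outcome lies outside the multiplicity procedure in SAP 4.1 and is modelled only if numbers allow (SAP 6.2.1). Deaths and secondary hospitalisations are reported as harms as well (SAP 6.5), though that does not repair the Day 28 endpoint.

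**Conclusion.** The point holds as a defect in a stated rule for a secondary outcome. On its most natural reading, SAP 6.1.2.2 omits later deaths and readmissions of children whose Day 7 form reports only an appropriate admission, and it departs from protocol 8.1.1. If the authors meant no severe complication, there is no loss, but the SAP has to say so.

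The under-count can arise in all arms. A tilt towards the intervention is conditional on the admission rise and on the 0.77 threshold for later risk. With equal later risk of 1% to 10%, the bias is 0.0045 to 0.045 percentage points, or about 1% to 14% of the 0.33-point difference the trial is designed to detect on the Day 7 outcome (0.0045 / 0.33 and 0.045 / 0.33). That is modest, but avoidable with data already being collected. Neither primary outcome is shown to be affected.

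**What to change.** In SAP 6.1.2.2, read both the Day 7 and Day 28 forms for every child, plus unscheduled visits for deaths, and classify each death and admission by its date. At minimum, replace the undefined condition in the second and third sources with *no death and no secondary hospitalisation was reported*. State that this follows protocol 8.1.1.

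Do not add hospital records as a source for this outcome. They are collected selectively, for children reported to have attended or been admitted to hospital and for referred children lost to follow-up (protocol 6.5.1, 8.1.1 and 8.2.4), so they would bring unequal ascertainment. No change to 6.1.2.1 is needed on this ground.

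The cost is a short SAP wording change and simple programming. No new data are needed, because Day 28 follow-up is already planned for every child.
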